- ii.* **Random assignment procedure:** Random assignment was conducted prior to the administration of the baseline *Participant Questionnaire* at each school. A lead research analyst used an existing algorithm available in Stata (random allocation command, *ralloc*) to generate a list of random assignments based on the total number of students who met eligibility criteria and were enrolled in the study. The list of eligible and enrolled students was alphabetized by last and then first name. The alphabetized student list was then paired with the random assignment list. This is when random assignment occurred – when a student name was associated with a treatment condition. Random assignment blocks of varying sizes assigned participants to the treatment or control condition at an equal (i.e., 1:1) assignment ratio within each participating school. The allocation lists are password-protected and stored on a secure PRG server and were also shared with each individual school so that administrators could ensure that students assigned to the treatment condition were pulled out of class during each *PGC* outreach session to receive the intervention.

The research analyst for the study prepared a *Study Roster* for each school, which listed the full name of each student, the condition to which the student was assigned, and associated a unique five-digit study ID with each student.

For both baseline and follow-up data collection, the study team prepares paper questionnaires pre-printed with each unique study ID number and organizes them according to school. During questionnaire administration, the study team ensures that each individual student receives the instrument with his or her assigned unique ID number. This number is associated with the participant's questionnaire data.²

- iii. **Blocking procedures:** Blocking occurs at the school level. Participants are enrolled and randomized at the individual level within each participating study school.
 - iv. **Probability of assignment to treatment group:** The probability of assignment to the treatment group is intended to be equal to the probability of assignment to the control condition; that is, p (assignment to treatment) = .5.

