The analytic sample is defined as all participants who were randomized into either the treatment or control conditions (as described in section 3b above) and who have reported sufficient outcome and covariate data.⁸ Missing data procedures are outlined in subsection 4cv below.

- c. **Data cleaning:** Prior to analysis, PRG staff will systematically screen or review the analytic variables (baseline and outcome) to identify errors, inconsistencies, missingness, and unreliable data.⁹ New variables are created in which data that are deemed unusable (i.e., invalid or unreliable) are coded as missing and flagged according to missing data type; all other data are retained, unchanged.¹⁰ The steps taken in this data cleaning process are outlined below.
 - i. **Identify and flag unreliable cases:** The first step in the data screening process is to identify and flag entire cases (i.e., entire questionnaires) that are unreliable. By unreliable, we mean that we have sufficient reason to believe that the respondent's answers are not honest representations of their behaviors, knowledge, and beliefs. These cases are treated as missing and excluded from our benchmark analyses.

Cases are flagged as unreliable when responses follow a clear, deliberate pattern. This data cleaning procedure is informed by the data processing rules established for the National Survey on Drug Use and Drug Health (NSDUDH) and for the Youth Risk Behavior Survey (YRBS), which treat records that follow defined patterns of responses

⁷ The alternative response to this first question is *I have never had sexual contact*. If a participant selects this response, they are skipped out of the subsequent question, *How many sexual partners have you had in the past 3 months?*

⁸ As outlined in subsection 4cv, our benchmark approach is to impute baseline/covariate data. As such, sufficient baseline/covariate data means all cases where data are not unit missing. We do not anticipate that we will have different analytic samples for our outcomes of interest; data are expected to be missing entirely for any given respondent at any observation point or not. If for whatever reason analytic samples are different for different outcomes, we will assess baseline equivalence separately for each analytic sample.

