¹⁷ We will code missing responses with a unique missing code that identifies or flags these missing values according to the reason they are missing (i.e., nonresponse, invalid, inconsistent). Unreliable data are not recoded to missing, rather cases deemed unreliable are coded as 1 in an indicator variable, treated as unit missing, and excluded from analysis. See the *Data cleaning* section or Table 3 in the Appendix for details on how missing data are coded.

¹⁸ For item missing values, we will only report prevalence of missing and inconsistent data for variables that are included in our model specifications and could therefore influence the constitution of the analytic sample.

5. Determine if any individuals who are in the randomized sample (for each outcome) are missing baseline covariates or the baseline measure of the outcome variable. If this is the case, our proposed benchmark approach is to use dummy variable adjustment procedures, as we feel it is the most straightforward and prudent approach for missing baseline/covariate data recommended in Puma et al. (2009).
 6. Conduct sensitivity analyses by estimating results with missing baseline data excluded from the analysis (i.e., use case-wise deletion for all cases with missing baseline and outcome data). In an appendix, we will report our benchmark results next to the sensitivity analysis results to verify findings.
- d. **Assessment of baseline equivalence:** Baseline equivalence will be reported for all baseline measures of each outcome variable as well as relevant demographic and sexual behavioral measures. We first list and describe the measures we will use to examine the equivalence of our treatment and control group at baseline. After we identify the measures, we provide details on the diagnostic methods that we will use to assess any baseline difference that may exist between the treatment and control groups in the measures outlined below.

Demographic and Sexual Behavior Measures

Baseline equivalence will be assessed for four demographic variables (identified below). Age, race, ethnicity and education are constructed using participant self-responses to questions in the baseline *Participant Questionnaire*. For the race variables, categorical responses to a single question are used to create multiple dichotomous variables. We provide details on variable coding below; details on variable construction can be found in Table 2 in the Appendix.

Demographic:

- Age (continuous)¹⁹
- Gender²⁰

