We propose to assess baseline equivalence of the treatment and control groups according to a multi-step procedure. Baseline equivalence statistics will be produced for each analytic sample.²² Only participants who provide baseline data to an outcome measure will be included in the analytic sample for that same outcome measure; thus the analytic sample used for each research question may vary slightly because of the exclusion of non-responders. As required by the “Identifying Programs that Impact Teen Pregnancy, Sexually Transmitted Infections, and Associated Sexual Risk Behaviors” review protocol, we will report the adjusted means and p-values of the differences in the baseline variable of interest for the treatment and control groups.²³ We will also report the standardized mean difference of each baseline variable for the treatment and control groups. This last statistic is not required by the review protocol but it is more consistent with the literature on balance statistics.²⁴

To establish baseline equivalence, we propose to generate model-based point estimates of the difference between the treatment and control groups for the identified baseline equivalence variables. We will report the adjusted means and p-values of the differences in the baseline variable of interest for the treatment and control groups. We will then compute the pooled standard deviation of these variables. Finally, we will produce a standardized difference of means by dividing the first term by the second.²⁵

step 1. First, we generate a model-based estimate of the difference between treatment and comparison groups on the pre-intervention measures identified above. Separate models will be run for each of the variables. The empirical model will be estimated with OLS (using Stata). If the measure is dichotomous, we propose to use a linear probability model to estimate the predicted probability of group membership. The model is a reduced-form variation of the model that we use to estimate program impact (as detailed in the *Model specification and covariates* section, below).²⁶

$$Y_{baseline} = \beta_0 + \beta_1 T + \sum (\beta_p X_p) + \varepsilon$$

where:

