$Y_{baseline}$ – is the baseline measure of the variable that we use to establish baseline equivalency (identified in the Appendix – Table 2 above). This variable is included as a covariate in the analytic model (see Table 2 in the Appendix for details on variable coding). Separate models will be estimated for each baseline equivalency measure specified above.

T – A dummy treatment indicator variable whose value equals 1 if the participant is randomized into the treatment group and zero otherwise.

²² Due to item missing outcome data, we expect there may be slight differences in analytic samples for each research question.

²³ Goesling, B., & Trenholm, C. (2016). Identifying Programs that Impact Teen Pregnancy, Sexually Transmitted Infections, and Associated Sexual Risk Behaviors. Mathematica Policy Research.

²⁴ The literature on balance statistics argues that significance testing is inappropriate for this diagnostic task (Austin, 2007; Imai et al., 2008; Austin, 2009; Stuart, 2010). Hypothesis tests can be misleading diagnostic measures of baseline equivalence because they conflate balance with statistical power.

²⁵ Note that we will produce diagnostic estimates of baseline equivalence on the exact same samples of observations that we will use in our primary analysis. In other words, we will apply the missing data approach outlined in section 4cv prior to producing estimates of baseline equivalency on the pre-intervention measures.

²⁶ It is a reduced- form because individual-level, demographic covariates are omitted. It is a variation because the dependent variable is the baseline equivalence variable, not the outcome measure.

X – School (blocking variable) – An $n-1$ vector of school indicator dummy variables that are coded one if the intervention was delivered at school n and coded zero otherwise.

β_0 – The intercept term, which represents the adjusted mean value of the baseline equivalency measure for participants in the control sample, with all other variables in the model held constant at zero.

β_1 – This represents the adjusted (but not standardized) mean difference in the baseline equivalency variable between treatment and control participants.

ε – The residual or random variation that remains for each observation after the structural components of the model are estimated. It is the difference between the observed and the predicted values at the individual level.

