The study is an individual randomized controlled trial in which eligible, consenting 9th-grade participants who volunteer to be pulled out of their regularly scheduled classes are randomly assigned by the evaluator to intervention (PGC) or control (business as usual) groups at a one-to-one ratio. The unit of assignment is the individual, and random assignment occurs after obtaining evaluation consent and assent and before the provision of any programming or collection of baseline data. Study participants are not informed that they are in the treatment or comparison group before baseline data collection. However, it is likely that some students will be aware of their PGC participation status before baseline data collection. In many schools, students will receive their schedules before baseline, and the schedules will include notation that a class is a PGC pullout class.

Youth in the intervention and comparison groups will receive a baseline survey and youth enrolled in the 2016-17 school year will receive a 12-month follow-up survey. Baseline data collection occurs during the fall of their 9th-grade year (before the provision of any PGC programming); follow-up data collection occurs during the fall of the 10th-grade year and will only be completed for study participants enrolled during the 2016-17 school year due to the shortened project period ending June 2018. In-school data collection is the preferred method of data collection for all data collection time points. If students no longer attend the study school or miss all available make-up administrations, they are offered the questionnaire first through an online administration, and then through mail. If students no longer attending the school do not complete an online or mail questionnaire, evaluation staff will attempt to conduct a phone interview using an abbreviated version of the questionnaire. Data collection procedures are the same for treatment and comparison groups.

For the implementation evaluation, PGC program staff will collect data on fidelity and adaptations, attendance, and quality. Staff will collect these data through observation forms, questionnaires, and attendance logs. PGC program staff (Center for Supportive Schools) complete the observations forms, school staff and students complete questionnaires, and attendance records are obtained from the school and maintained by PGC program staff.

Schedule/Timeline

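### Section 4d and footnote 8 exclude students whom the missing-data rules keep, and the attrition formulas in 4f.ii do not describe the analysed sample

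*Combined protocol and SAP*

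**What the plan says.** **Who is analysed.** Section 4d (Balance Assessment Methods) says: "Only participants who provide baseline data to an outcome measure will be included in the analytic sample for that same outcome measure". Footnote 25 says that balance is assessed "on the exact same samples of observations that we will use in our primary analysis". Section 4b defines the sample as randomised students with sufficient outcome and covariate data, and footnote 8 explains that "sufficient baseline/covariate data means all cases where data are not unit missing". Step 5 of section 4c.v takes randomised students who "are missing baseline covariates or the baseline measure of the outcome variable" and says that "our proposed benchmark approach is to use dummy variable adjustment procedures". Step 6 and sensitivity analysis 2 in 4f.iv make deletion for missing baseline a sensitivity analysis. The short summaries in 4c.ii and 4c.iv also adjust missing baseline values and keep the student. The opening of 4f keeps all randomised students apart from those lost to attrition. Table 1 makes tenth-grade data the only condition for each outcome.

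**How attrition is measured.** Section 4f.ii defines overall and differential attrition as one minus completed tenth-grade questionnaires over students enrolled. Sections 4c.i to 4c.iv set unreliable questionnaires, invalid values and inconsistent answers to missing, or treat them as missing. Step 4 of 4c.v deletes students without outcome data. Section 3d leaves out questionnaires completed after the window closes.

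**The concern.** The primary sample should be identifiable from the plan before the data are analysed, and here it is not. Under the 4d sentence, deletion for a missing baseline outcome would already be the primary analysis, so step 6 and sensitivity analysis 2 would test little for that variable.

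The choice bears on validity. Section 3b.ii says: "Random assignment was conducted prior to the administration of the baseline" questionnaire. The Evaluation Abstract (Research Design and Data Collection) says that students were not told their group by the study before baseline, but also that "it is likely that some students will be aware of their PGC participation status before baseline data collection", for example from class schedules. Whether a student completed the baseline questionnaire is therefore a post-randomisation event whose rate or mix could differ by arm. None of the six analyses in 4f.iv says that it restores students without a baseline questionnaire.

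Footnotes 4 and 29 rest the claim of unbiasedness on low attrition, and footnote 29 adds low differential attrition. A figure based on returned questionnaires does not show whether that condition holds for the students analysed.

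**Working it through.** The documents give no attrition, missing-data or cleaning rates, so there is no stated figure to reproduce. The check is a comparison of the text, followed by arithmetic on assumed rates.

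**1. Rules side by side**

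| Place | Baseline outcome item missing | No baseline questionnaire |
|---|---|---|
| 4d, Balance Assessment Methods | out | out |
| 4b, footnote 8 | in | out |
| 4c.v, step 5 | in, dummy adjustment | in (no exception stated) |
| 4c.v step 6; 4f.iv analysis 2 | out as sensitivity analysis only | not distinguished |
| 4c.ii and 4c.iv summaries | in | not distinguished |
| 4f opening; Table 1 | in | in on its face |

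For item-missing baselines, the 4d sentence stands alone against all the rest. For a wholly missing baseline, footnote 8 and step 5 differ, and correcting 4d does not settle it.

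**2. Attrition.** Let a be the share not responding at tenth grade and e the share of completers whose outcome is removed by cleaning or left unanswered.

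- Plan's formula: a. Loss from the analysed sample: 1 - (1 - a)(1 - e). Understatement: (1 - a)e.
- Assumed a = 15%: e = 1%, 2% or 4% gives 0.85, 1.7 or 3.4 points. On the roughly 1,600 students projected in the Evaluation Abstract, that is about 14, 27 or 54 students.
- Differential, a = 15% in both arms, e = 3% in PGC and 1% in control: 17.55% - 15.85% = 1.7 points, where the formula shows 0.
- Differential, a = 16% and 14%, e = 2% and 4%: 17.68% - 17.44% = 0.24 points, where the formula shows 2.0. The error can go either way.

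One route into e acts directly on a primary outcome. A student who reports sexual initiation at baseline and denies it at tenth grade has both values set to missing under 4c.iv, and so leaves the initiation analysis despite completing the questionnaire.

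**3. Bias from excluding students with missing baseline.** Let b be the missing-baseline rate in an arm and D the gap in tenth-grade initiation between missing-baseline and other students in that arm. The target is the arm difference among all students with a tenth-grade value.

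- Exclusion: bias = bC·DC - bT·DT.
- Dummy adjustment: bias = w(DT - DC) - (bT·DT - bC·DC), where w is the regression weight of the missing-baseline stratum (w = b when the rates are equal).
- No covariates, full sample: bias = 0.

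| Assumed bT/bC | Assumed DT/DC (points) | Exclusion | Dummy | No covariates |
|---|---|---|---|---|
| 10%/10% | 20/20 | 0 | 0 | 0 |
| 10%/10% | 20/0 | -2.0 | 0 | 0 |
| 12%/8% | 20/20 | -0.8 | -0.8 | 0 |

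Entries are in percentage points; a negative sign favours PGC. A simulation with 1,360 students (85% of 1,600) and 4,000 replicates agreed with all nine entries within Monte Carlo error (standard error 0.04 points). The third row gave -0.77, -0.77 and 0.04.

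**The case against.** The strongest reply is that the plan's intention is clear. Step 5, step 6, the summaries in 4c.ii and 4c.iv, the opening of 4f and Table 1 all point to keeping students with missing baseline. Footnote 25 goes on to say that the 4c.v rules are applied before balance is assessed. Footnote 22, attached to the same paragraph of 4d, gives a different reason for varying samples: "Due to item missing outcome data, we expect there may be slight differences in analytic samples for each research question". On item-missing baselines this stands: the 4d sentence is probably a drafting slip. It still has to be corrected, and the reply does not settle footnote 8's exclusion of students with no baseline questionnaire.

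On attrition, step 2 and footnote 9 report missing, inconsistent, unreliable and invalid data by arm, and step 4 links attrition statistics to students without outcome data. A reader could rebuild part of the loss. That too stands, but no attrition figure for the analysed sample is defined.

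Three stronger readings are not supported:

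- A reader might infer that footnote 8 sides with 4d. It does so only for wholly missing baselines; on missing items it agrees with step 5.
- A reader might infer that logical imputation under step 3 could bring non-completers back, so that the formulas overstate loss. Table 3 allows logical editing only for an unanswered item, and step 4 deletes students without outcome data.
- A reader might infer that dummy adjustment cures the bias. It does not when missing-baseline rates differ by arm.

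**Conclusion.** The point holds as a matter of specification and reporting. Followed as written, 4d makes an avoidable post-randomisation exclusion the primary analysis. With 4d corrected, footnote 8 still does so for students with no baseline questionnaire. The 4f.ii formulas can understate overall loss and can misstate differential loss in either direction for each outcome.

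The size is unknown. If missing-baseline rates and outcome gaps are equal by arm, the exclusion bias is about zero. The 2-point case needs a 20-point gap in one arm and none in the other, and nothing in the documents suggests this. With equal gaps of 10 to 20 points and rates differing by 2 to 4 points, the bias is 0.2 to 0.8 points (0.02 × 10 to 0.04 × 20). The attrition understatement is (1 - a)e, or 1.7 points at the assumed 15% and 2%. The documents do not show that a bias will occur, only that the plan leaves room for one and would not reveal it. This should be fixed before analysis.

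**What to change.** - Correct the 4d sentence and the clause of footnote 8 on unit-missing data, so that 4b, 4c.v, 4d, 4f and Table 1 state one primary sample per outcome: every randomised student with a usable tenth-grade value from within the window. Handle missing baseline, whether an item or the whole questionnaire, by the plan's dummy adjustment. Keep case-wise deletion as the step 6 sensitivity analysis.
- State that sensitivity analysis 1 (no covariates) uses this same full sample, since it does not condition on a missing-baseline indicator. Report missing-baseline rates by arm.
- If the team prefers to keep footnote 8's exclusion, say so in every section and count those students as attrition.
- In 4f.ii add, for each outcome and by arm, 1 - (analysed n / randomised n), overall and differential, next to questionnaire non-response.

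The cost is SAP wording and slightly more reporting: a row per outcome in the attrition table and the missing-baseline rates. No new data or model is needed. Reported attrition may look slightly less favourable.

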- c) Race – race of participant as self-reported at baseline. Race will be coded as a set of 4-1 = 3 dummy variables (each coded as 1 if they are of the specified race and coded as 0 otherwise); each of the variables will be re-centered at the grand mean for analysis.
- d) Hispanic/Latino – self-reported as Hispanic, Latino, or of Spanish origin at baseline (0=do not identify as Hispanic/Latino/Spanish origin; 1=identify as Hispanic, Latino, of Spanish origin); variable will be re-centered at the grand mean for analysis.
- e) School – An $n-1$ vector of school indicator dummy variables that are coded one if the intervention was delivered at school n and coded zero otherwise. School 1 is the reference category and is excluded from analysis. The dummy variables will be mean-centered for analysis to facilitate interpretation.

β_0 – The intercept term, which represents, depending on the outcome measure of interest in the analysis, the outcome for the average control participant with all other variables in the model held constant at their mean.

β_1 – This is the parameter estimate of substantive interest. β_1 represents, depending on the outcome measure of interest in the analysis, either: 1) the adjusted mean difference in treatment and control participants’ self-reported sexual initiation at the 10th follow-up; 2) the adjusted mean difference in treatment and control participants’ self-reported times having sex in the past three months at the 10th grade follow-up; or 3) the adjusted mean difference in treatment and control participants’ self-reported number of sexual partners in the past three months at the 10th follow-up.

ε – The error term or unexplained individual-level variance that remains for each observation after the structural components of the model are estimated. It is the difference between the observed and the predicted values at the individual level.

We will report model-estimated effects and the results of significance tests in the findings section of the final impact report. Statistical significance will be based on test statistics produced by Stata for the coefficient β_1 using a two-tailed test, with $p < .05$.

- ii. **Sample attrition:** Overall and differential attrition will be calculated using the full sample of students enrolled in the study. This will be determined using data within the *Questionnaire Completion Database*. We will calculate overall attrition using the following formula:

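### Baseline-equivalence statistics are computed with constant-filled baseline values as the dependent variable, so age, gender and some baseline outcome rows do not describe the observed data

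*Combined protocol and SAP*

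**What the plan says.** Section 4d checks balance on age, gender, race, Hispanic/Latino and the three baseline outcome measures. Step 1 regresses each measure on treatment and school indicators. Footnote 26 calls this model "reduced- form because individual-level, demographic covariates are omitted". Steps 2 to 4 report adjusted means and p-values, a pooled SD, and Hedges' g or, for dichotomous measures, the Cox index.

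On missing values:
- Footnote 25 to 4d: "we will apply the missing data approach outlined in section 4cv prior to producing estimates of baseline equivalency".
- 4cv, step 5, for missing baseline values: "our proposed benchmark approach is to use dummy variable adjustment procedures". Neither the constant nor the indicator is written out.
- Footnote 8 to 4b: "sufficient baseline/covariate data means all cases where data are not unit missing". A participant who skipped one baseline item stays in.
- 4d, Balance Assessment Methods: "Only participants who provide baseline data to an outcome measure will be included in the analytic sample for that same outcome measure". This is a narrower rule.
- 4f.iv, item 2, promises equivalence results with and without the adjustment, but only for the pre-intervention outcome variables.

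On school coding, step 1 of 4d uses "indicator dummy variables that are coded one if the intervention was delivered at school" n and zero otherwise, and defines the intercept as the control sample's adjusted mean "with all other variables in the model held constant at zero". For the impact model, 4f.i says: "The dummy variables will be mean-centered for analysis to facilitate interpretation". Table 2 also centres them.

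**The concern.** Dummy variable adjustment is a device for covariates: the indicator takes up whatever constant was inserted, so the constant does no harm to the treatment coefficient. That protection is lost when the filled variable moves to the left-hand side. There the constant is treated as a measurement and enters both arm means, their difference and the pooled SD.

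The consequence can go either way. A real imbalance can be diluted, or a difference in item non-response between arms can appear as an imbalance in the characteristic. The plan deletes cases with missing outcomes and regards missing data as a major threat to validity, so readers will use this table to judge whether the remaining arms are comparable. It should describe what participants reported.

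A smaller matter sits beside this. With 0/1 school dummies and everything held at zero, the step 1 intercept is the fitted control mean at the reference school, not in the control sample.

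**Working it through.** The documents give no equivalence result, missingness rate or fill constant, so there is no stated figure to reproduce. All rates, means and SDs below are assumptions.

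**1. Which rows can contain filled values.** Race has its own category for no selection, and Hispanic/Latino is 0 when not selected (4d footnote 21, Table 2), so neither needs much filling. Age and gender have no such code. For baseline outcomes, the narrower 4d rule removes filled values from a sample's own baseline measure. It does not remove, say, missing baseline sexual initiation from the number-of-partners sample, and 4d produces the statistics for each analytic sample.

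**2. Formula.** Let a share m be missing in each arm, with true difference δ, SD s, mean μ and constant c. After filling:
- difference = (1−m)δ
- variance = (1−m)s² + m(1−m)(μ−c)²

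If c is the mean, the last term is close to zero and g is multiplied by (1−m)/√(1−m) = √(1−m). The loss, 1−√(1−m), is 2.5%, 5% and 11% at m = 5%, 10% and 20%.

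**3. Age, assumed mean 14.5, SD 0.6, true g = 0.25 (δ = 0.15 years).**

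| Missing, both arms | g, mean fill | g, raw age filled with 0 |
|---|---|---|
| 2% | 0.247 | 0.069 |
| 5% | 0.243 | 0.044 |
| 10% | 0.237 | 0.031 |
| 20% | 0.223 | 0.020 |

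At 5% with zero fill, the difference is 0.95 × 0.15 = 0.143, the pooled SD is 3.23, and the ratio is 0.044.

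**4. Unequal missingness, true difference 0.** The false difference is (m_c − m_t)(μ − c). With zero fill, 6% missing in treatment and 4% in control, it is −0.02 × 14.5 = −0.29 years. The variances are 0.94×0.36 + 0.06×0.94×14.5² = 12.20 and 0.96×0.36 + 0.04×0.96×14.5² = 8.42. The pooled SD is about √10.31 = 3.21, so g = −0.09. Mean fill gives 0.

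**5. Dichotomous measure, assumed 20% versus 15%.** The true Cox index is (logit 0.20 − logit 0.15)/1.65 = 0.211. At 10% missing it reads 0.207 after zero fill and 0.190 after mean fill.

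**6. p-values.** Ignoring school, t is proportional to g√n. Under mean fill with equal missingness, g falls by √(1−m), but n counts the filled cases and so exceeds the observed n by a factor 1/(1−m). The two cancel, and p stays close to its observed-data value. Under zero fill of raw age at 5%, t falls to about 0.044/(0.25×√0.95) = 18% of its observed-data value.

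**7. Would adding an indicator to step 1 do?** In one simulated data set (18 schools, N = 1,600, missingness about 8% in control and 11% in treatment), the treatment coefficient was 0.045 in observed cases, 0.033 after zero fill, and 0.039 after zero fill plus an indicator. The indicator did not restore the observed-case estimate.

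**8. School coding.** In the same simulation without missing data, with school rates spread from 5% to 35%, the intercept was 0.032 with 0/1 dummies and 0.211 with centred dummies (raw control mean 0.211). The treatment coefficient (0.0441) and p-value (0.033) were identical under both. Only if the Cox probabilities were taken from the coefficients would the index change: 0.558 against 0.150.

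**The case against.** Much can be said for the plan, and several stronger readings do not stand.

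- **Zero-filled age is not the likely result.** 4f.i re-centres age at its grand mean, and zero on that scale is mean fill. At 5% missing that costs 2.5% of the standardised difference. This stands: the zero-fill figures bound the damage and do not predict it.
- **Little may need filling.** Step 3 of 4cv imputes logically from related items first, and footnote 8 expects data to be missing for a whole questionnaire or not at all. This is fair, but invalid baseline values are also set to missing and then adjusted (4c.ii, Table 3), and no rate is given.
- **The baseline outcomes are covered.** The narrower 4d rule would protect each sample's own baseline measure, and an unadjusted comparison is promised in an appendix. This stands in part. The rule conflicts with footnote 8, it does not reach the other outcomes' baseline measures, and the appendix leaves out age and gender.
- **The intercept.** A reader might infer that the differences are wrong because the intercept belongs to one school. They are not: school coding cannot change the differences, p-values or Hedges' g. The impact model and Table 2 centre the dummies, and 4d calls its model a variation of the impact model. What remains is an omission in step 1. Step 4 defines the Cox probabilities as those within each group and does not say that they come from the coefficients.
- **Consequence.** A reader might infer that this table is the only evidence of comparability, or that impact estimates are biased. Neither is supported. Overall and differential attrition are also reported, no decision rule hangs on the table, and it does not feed the impact model.

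**Conclusion.** The point holds for the equivalence table. Footnote 25, step 5 of 4cv and footnote 8 together make constant-filled values the dependent variable with no missing-data indicator, for age, gender, and baseline outcomes shown in another outcome's sample. This assumes dummy variable adjustment in its usual form. The size depends on a constant the plan does not state: under mean fill the effect is small and p-values barely move, while under zero fill of raw age the row would be meaningless. For a sample's own baseline outcome, the firm finding is a contradiction between footnote 8 and the 4d sample rule. The school-coding point is secondary: it touches the reported adjusted means, and the Cox index only if that is built from the coefficients.

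**What to change.** 1. Amend footnote 25. Keep the same analytic sample, but estimate each baseline variable's difference and pooled SD only in members with an observed value. Show n and percent missing by arm in the table; prevalence of missing data by arm is already to be reported elsewhere.
2. Reconcile footnotes 8 and 25 with the 4d rule on whether participants missing the baseline outcome belong in that outcome's sample.
3. In step 1, repeat that the school dummies are mean-centred, so that the adjusted control mean refers to the whole analytic sample. In step 4, state that the Cox index uses the group probabilities so obtained.

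This takes a few sentences and no new data. The price is that denominators will differ slightly between rows.
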